## 7.5 Analyses of the Clinical Trials

Further analyses of intervention effects on the defined primary and secondary endpoints of each trial using post-intervention data will include both cumulative effects examining the entire interval since randomization and analyses limited to the post-intervention period. The primary analysis strategies will be informed by those of the original protocol, under the intention-to-treat framework and will employ either the unweighted or weighted (2-sided) log rank statistic as originally described (The Women's Health Initiative Study Group, 1998). Such a statistic can be written

$$T = \sum w_i (O_i - E_i)$$

where  $w_i$  is the value of the weight function evaluated at the  $i^{\text{th}}$  largest time from randomization to clinical outcome event among women in both groups,  $O_i$  is one or zero depending on whether the outcome occurred in a woman in the treated group or not, and  $E_i$  is the conditional expected value of  $O_i$ , under the null hypothesis of no treatment effect. If  $V_i$  represents the conditional variance of  $O_i$ , then it follows from the uncorrelatedness of the elements of this summation that the variance ( $\sigma^2$ ) of  $T$  is estimated by  $\sigma^2 = \sum w_i^2 V_i$  and the test for differences between groups is then made by referring  $T^2/\sigma^2$  to the 95th percentile of a chi-square distribution on one degree of freedom.

The weighting was intended to enhance test power under the expectation that intervention versus control disease incidence ratios increase in absolute value approximately linearly as a function of time since randomization. The weights  $w_i$  were chosen to equal time from randomization up to a disease-specific maximum (three years for cardiovascular disease and fracture occurrence, 10 years for cancer occurrence and total mortality) and to be constant thereafter. Because this assumption was supported in some instances in the hormone trials and not in others, both weighted and unweighted statistics will be used, with unweighted statistics as the default test statistics unless a prior evidence had suggested otherwise (e.g., for effects on cancer incidence). In analyses of post-intervention effects, unweighted time to event analyses will be conducted, typically using date of the close-out visit (or date of official notification of study closure for the HT trials) as the "time zero" for these analyses.

Analyses of intervention effects will typically be stratified on baseline age (50-54, 55-59, 60-69, 70-79), and self-reported prevalent disease (if applicable) for that outcome, and the categories of the other interventions. The primary HT comparisons will be examined separately based on baseline WHI hysterectomy status.

To assess potential selection bias among Extension Study participants relative to the initial trial cohort, comparisons of demographics, health history, adherence to intervention and key outcome event rates will be made between Extension Study enrollees and non-enrollees using data from the initial WHI database. If an assumption of no selection bias is supported, women who did not consent to the Extension Study will be censored at their last follow-up contact during the original WHI study, except for total mortality analyses where vital status information will be obtained from the NDI. Methods to account for non-representative enrollment using inverse sampling probability weighted tests may be employed if there is evidence of noteworthy selection in Extension Study enrollment.

All analyses of clinical trial results will be reported as two-sided tests with acknowledgement of multiple testing issues, either by appropriate adjustment of p-values and confidence intervals or by an acknowledgement of the number of tests performed.

More detailed explanatory analyses will include tests for group differences with concomitant adjustment for covariates, as well as explanatory analyses that examine the extent to which an intervention benefit can be explained by changes in intermediate variables and outcomes (e.g., nutritional and biochemical measurements). These analyses will be conducted using relative risk regression methods, with appropriate account of measurement error in the intermediate variable measurements as necessary, using data obtained in the aforementioned reliability sub-study. Nested case-control and case-cohort sampling procedures (see next subsection) will be used in most such analyses since stored materials used to determine immediate variable values will not be routinely analyzed for the entire CT cohort.

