## **4. Study Design**

### **4.1 Overview**

The original WHI design was composed of two primary study components, a partial factorial randomized clinical trial and an observational study. Women participating in the CT accepted randomization into the DM or HT trials (or both). After one year of CT participation, they were offered randomization into the CaD trial. Women not eligible or interested in the CT were offered enrollment into the OS. For the continuation of the WHI Extension Study, participating women will continued to be associated with the same study component(s) to which they were originally enrolled.

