#### WHI CT Partial Factorial Design

Number of women enrolled in the original trial WHI components  
(Numbers in parentheses represent enrollment in the CaD trial)

			HT (CaD)				Not Randomized
			Intact Uterus				
			Yes		No		
			E+P	Placebo	E-alone	Placebo	
			8,506	8,102	5,310	5,429	40,785 (20,193)
DM (CaD)	Intervention	19,541 (9,645)	972 (596)	925 (577)	615 (371)	670 (430)	16,359 (7,671)
	Control	29,294 (15,565)	1,457 (917)	1,304 (838)	1,039 (639)	1,068 (649)	24,426 (12,522)
	Not Randomized	19,297 (11,072)	6,077 (3,530)	5,873 (3,455)	3,656 (2,064)	3,691 (2,023)	
Total		68,132 (36,282)					

Number of women consenting to the 2005-2010 Extension Study by original WHI trial components  
(Numbers in parentheses represent original CaD trial enrollment)

			HT (CaD)				Not Randomized
			Intact Uterus				
			Yes		No		
			E+P	Placebo	E-alone	Placebo	
			6,545	6,243	3,778	3,867	31,743 (16,946)
DM (CaD)	Intervention	14,769 (7,920)	741 (493)	712 (466)	448 (286)	499 (337)	12,369 (6,338)
	Control	23,089 (13,090)	1,140 (756)	1,028 (714)	753 (494)	794 (518)	19,374 (10,608)
	Not Randomized	14,318 (8,852)	4,664 (2,887)	4,503 (2,817)	2,577 (1,598)	2,574 (1,550)	
Total		52,176 (29,862)					

Power calculations pertinent to the combined CT and OS as a cohort study for a range of sample sizes that may represent either the entire cohort or key component specific or racial/ethnic subgroups are included in Appendix B.

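### The default strata in section 7.5 take in calcium/vitamin D (CaD) status, which is set a year after DM randomisation and was taken up differently by DM arm (49.4% vs 53.1%)

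*Protocol*

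**What the plan says.** Section 7.5 of the protocol sets the default strata for the clinical trial comparisons. The first factor is age, in four bands: "Analyses of intervention effects will typically be stratified on baseline age (50-54, 55-59, 60-69, 70-79"). Two further factors complete the list: "and self-reported prevalent disease (if applicable) for that outcome, and the categories of the other interventions". CaD is neither named nor excluded. Section 2 describes the clinical trial as having three components (DM, HT and CaD), so for a DM or HT analysis the other interventions include CaD on a plain reading.

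The same section places these analyses "under the intention-to-treat framework" and includes "cumulative effects examining the entire interval since randomization".

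Section 4.1 gives the order of events. Entry to the clinical trial came first: "Women participating in the CT accepted randomization into the DM or HT trials (or both"). The CaD step is described as a later one: "After one year of CT participation, they were offered randomization into the CaD trial".

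The factorial table in Figure 1 prints CaD enrolment in brackets beside each cell ("Numbers in parentheses represent enrollment in the CaD trial"). No section limits CaD strata to time after CaD randomisation or comments on uptake by arm.

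**The concern.** A stratification factor is safe in an intention-to-treat comparison if it was fixed before, or at, the randomisation being analysed. Age, prevalent disease and the other of HT/DM meet that test for an HT or DM analysis. CaD status does not. It is settled about a year later, by a voluntary decision that the first assignment may influence.

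If assignment did influence it, the women in a given CaD category no longer form randomised groups with respect to DM. Some women would have joined CaD in one DM arm but not in the other. If their risk differs from that of the women they are grouped with, the stratified comparison is biased even when DM has no effect. The bias is systematic, so longer follow-up does not remove it, and longer follow-up is the purpose of the Extension Study.

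**Working it through.** **Step 1. Check the table.** The cells of the original-enrolment table in Figure 1 add up to the printed margins: DM intervention 19,541 (9,645), DM control 29,294 (15,565), not in DM 19,297 (11,072), total 68,132 (36,282).

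**Step 2. CaD uptake by arm.** Uptake = CaD count / number enrolled.

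| Comparison | Intervention or active | Control or placebo | Difference | p |
|---|---|---|---|---|
| DM, all | 9,645/19,541 = 49.36% | 15,565/29,294 = 53.13% | -3.78 points | 3e-16 |
| DM, not in HT | 7,671/16,359 = 46.89% | 12,522/24,426 = 51.27% | -4.37 | 5e-18 |
| DM, also in HT | 1,974/3,182 = 62.04% | 3,043/4,868 = 62.51% | -0.47 | 0.67 |
| E+P | 5,043/8,506 = 59.29% | 4,870/8,102 = 60.11% | -0.82 | 0.28 |
| E-alone | 3,074/5,310 = 57.89% | 3,102/5,429 = 57.14% | +0.75 | 0.43 |

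For DM overall, the pooled proportion is 25,210/48,835 = 0.5162. The standard error under equality is √[0.5162 × 0.4838 × (1/19,541 + 1/29,294)] = 0.00462, so z = -0.0378/0.00462 = -8.2. The 95% interval, with unpooled standard error 0.00461, is -4.7 to -2.9 points. Among women who consented to the 2005-2010 Extension, the gap persists: 7,920/14,769 = 53.6% against 13,090/23,089 = 56.7%.

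**Step 3. What this does to a null DM effect.** Assume no woman joins CaD only because she was assigned to DM intervention. Three groups then follow from the uptake figures:
- A, would join in either arm: 0.4936
- S, would join only if assigned to control: 0.5313 - 0.4936 = 0.0378
- N, would never join: 1 - 0.5313 = 0.4687

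Give group N risk 1 and group A risk r. The documents do not report r, so it is varied from 1.0 to 0.5. First give group S the same risk as A. Among CaD joiners, both arms then have risk r and the hazard ratio is 1. Among non-joiners, the intervention arm holds S and N and the control arm holds N only, so

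HR(non-joiners) = (S·r + N)/(S + N).

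At r = 0.7 this is (0.0378 × 0.7 + 0.4687)/0.5064 = 0.978.

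The two log hazard ratios are pooled with information weights, w = expected events × f(1 - f), where f is the intervention share of the stratum:
- Joiners: f = 9,645/25,210 = 0.3826; events proportional to 0.7 × 25,210 = 17,647; w ≈ 4,168
- Non-joiners: f = 9,896/23,625 = 0.4189; events proportional to 9,896 × 0.9776 + 13,729 ≈ 23,404; w ≈ 5,697

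Pooled log HR = 5,697 × ln(0.9776)/(4,168 + 5,697) = -0.0131, so the pooled HR is 0.987.

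| r (joiners vs non-joiners) | Pooled DM HR under no effect |
|---|---|
| 1.0 | 1.000 |
| 0.8 | 0.992 |
| 0.7 | 0.987 |
| 0.6 | 0.982 |
| 0.5 | 0.975 |

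Changing the risk of group S hardly moves the pooled value. Giving S the risk of N, the midpoint, 1.5, or half of r leaves it at 0.991 to 0.992 for r = 0.8 and 0.975 to 0.976 for r = 0.5.

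**Step 4. With the fix.** Stratifying only on factors fixed at DM randomisation gives 1.000 under no effect, by randomisation.

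**The case against.** **The rule is a soft default.** Section 7.5 says typically, does not name CaD, and does not say whether strata are fixed or time-dependent. It also says that strategies are informed by the original protocol, which is not shown. All of this stands, and it limits how firmly one can say what will be run. But the section does set a list of factors, and its plain reading takes in CaD. That is worth closing off.

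**A reader might infer that the HT results are biased too.** The documents do not support that. CaD uptake is balanced in both hormone comparisons (p = 0.28 and 0.43). Objective 2, the one objective about effects of the original interventions, concerns hormones only. The demonstrated imbalance is confined to DM, and within DM to women not in HT.

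**A reader might infer that CaD strata contain no first-year events.** That follows only for death. Nothing in the protocol says that a non-fatal first-year event kept a woman out of CaD. In the analyses limited to the post-intervention period, time zero is close-out or notification of study closure, by which time CaD status was generally settled. Differential uptake by DM arm does not depend on this argument.

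**A reader might infer large distortions inside CaD strata.** Section 7.5 promises a stratified test pooled over strata, not DM effects by CaD category. The size within strata is also model-dependent. The three-group model gives about 0.88 to 1.04 across the risks tried for group S. A two-class frailty model gives only 0.987 to 0.998 within strata and 0.988 to 0.998 pooled. That model assumes frailty prevalence 20-50%, frailty hazard ratio 2-3, one uptake odds ratio of 0.3-0.6 common to both arms, 1% annual baseline hazard and 11 years from year 1. Neither set of assumptions can be checked from the documents.

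**There is a reason to adjust for CaD.** If CaD was allocated 1:1 (assumed), about 24.7% of the DM intervention arm and 26.6% of control received active CaD. The gap is under 2 points, and it is itself a consequence of DM assignment, so it belongs in the intention-to-treat effect.

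**Conclusion.** The point holds for DM at modest size. On its plain reading, the default in section 7.5 conditions the DM comparison on CaD uptake, which follows DM randomisation by a year and differed by arm well beyond chance (z = -8.2). Under no true effect, the pooled stratified DM hazard ratio would be about 0.975 to 0.992 if joiners carry 0.5 to 0.8 times the risk of non-joiners, a shift of roughly 1% to 2.5% towards apparent benefit. If joiners and non-joiners have equal risk, there is essentially no shift. That relative risk, and the three-group structure, are assumptions. The uptake difference is the protocol's own. For HT no bias is shown, and the argument is only that strata should be fixed at the randomisation under analysis.

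**What to change.** In section 7.5, state that the primary HT and DM analyses are stratified on baseline age, prevalent disease where applicable, and the other of HT/DM assignment, and that CaD status is not a stratum. CaD analyses keep HT and DM as strata, since both precede CaD randomisation.

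Label any HT or DM analysis that uses CaD status as a sensitivity or interaction analysis, whether CaD is entered as fixed or as time-dependent. A time-dependent CaD stratum deals with the first year but still conditions on the same uptake afterwards, so it should not become the primary analysis.

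The cost is one or two sentences, no new data, and little or no power. The small downside is that the modest difference between DM arms in CaD exposure stays inside the DM intention-to-treat effect. This should be said when the results are reported.

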## 2.2 Considerations for Additional Data Collection from HT Participants

In the first report from post-intervention follow-up for the E+P trial, no statistically significant increased cardiovascular risks were observed in the women assigned to CEE plus MPA as compared to women assigned to placebo, although point estimates suggested the possibility of some continuing adverse effects for stroke and venous thromboembolic disease (Heiss et al, 2008). The protective effect of E+P on fractures had also diminished (Heiss et al, 2008). Evidence of some dilution of E+P effects on breast cancer incidence was observed (Chlebowski et al, 2009) but a greater risk of fatal and nonfatal malignancies occurred after the intervention in the CEE plus MPA group and the global risk index remained significantly elevated in women randomly assigned to the combined hormone group (Heiss et al, 2008). While these reports on the early post-intervention period found few statistically significant effects, longer follow-up is needed to track the trajectory of these effects and determine whether there is persistent harm for stroke, VT, breast cancer and other cancer incidence and mortality as well as to examine any longer term effects of this 5-year intervention on women in their eighth and ninth decade.

Post-intervention follow-up of the E-alone trial through 2009 found no associations with risk of CHD, deep vein thrombosis, stroke, hip fracture, or colorectal cancer, but a nominally statistically significant decreased risk of breast cancer was observed over the mean 10.7 years of follow-up and median 5.9 years of CEE use (LaCroix et al, 2011). These findings reinforce the outcome-specific differences in hormone therapy effects.

Post intervention findings from the DM and CaD trials have not yet been published but will be developed on the complete database from the 2005-2010 Extension study..

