### **3. Study Objectives**

The primary objectives of the continuing WHI Extension Study are:

Objective 1: To study factors leading to an increased risk of CVD in older women of diverse race and ethnicity, including CHD, stroke, heart failure, atrial fibrillation, PAD, and VTE, and conversely to examine the factors that determine absence of CVD as part of successful aging.

Objective 2: To study the longer-term effects of estrogen plus progestin and estrogen alone on cardiovascular disease, cancer and fracture incidence and mortality.

Objective 3: To serve as a platform, at low incremental cost, for a new generation of prevention trials of lifestyle interventions or supplements affecting the overall health of older women.

Objective 4: To serve as a platform, at low incremental cost, for studies of the health of post-menopausal women as they age.

To achieve these objectives full outcomes ascertainment and documentation will occur annually in two important sub-cohorts of women—those in the hormone trials, plus African-American and Hispanic women—a target of 24,000 of whom 8,000 will be over age 80, and 10,000 will be racial/ethnic minorities. In addition, self-reported outcomes for the full range of health conditions will be collected annually from the entire cohort to support the same high quality documentation of their outcomes as funding permits.

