#### **Medical Records Cohort Specific Outcomes Collection Activities:**

Data from the scanned Form 33 will be made available electronically to Regional Centers for use in their subsequent outcomes documentation efforts. RC/OCS staff will review Form 33 from Medical Records Cohort members for completeness and for potential health events requiring retrieval of medical records. RC/OCS staff will telephone the participant, as needed, to clarify or complete responses on these questionnaires. If the participant has signed the Release of Information located on the back of Form 33, RC/OCS staff will use this form to obtain medical records for the designated events for participants in the Medical Records Cohort. If needed, RC/OCS staff will obtain an institution-specific release of information from the participant. RC/OCS staff will collect outcomes documentation and then assemble them into packets. They will label each document with the participant's study ID, electronically scan the entire outcomes packet, and forward the scanned documents to the CCC for review. The CCC will remove all confidential identifiers and forward the chart for subsequent adjudication according to existing procedures for adjudicating cases.

**Self-Report Cohort Specific Outcomes Collection Activities:** Data from the scanned Form 33 will be stored at the CCC for use as self-reported events. If funding becomes available, documentation and adjudication as described for the Medical Records Cohort may be implemented for selected outcomes or selected participants.

**Passive Follow-up:** At regular intervals, the CCC will obtain information on vital and health status for the entire cohort, as applicable, through accessing national databases such as the National Death Index (NDI), and the Center for Medicare and Medicaid Services (CMS), cancer registries, and large health maintenance organizations such as Kaiser Permanente. This information will be linked to the existing database for use in

studies to examine additional health outcomes, health care utilization and aspects of quality of care, and comparative effectiveness.

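### Section 7.5 uses the National Death Index for total mortality only, so cause-specific mortality stops following Extension non-consenters, about a fifth of eligible hormone-trial women, while total mortality continues

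*Protocol*

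**What the plan says.** Protocol Section 7.5 first compares Extension enrollees with non-enrollees on data from the initial WHI database. Two branches follow.

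- No selection found: "If an assumption of no selection bias is supported, women who did not consent to the Extension Study will be censored at their last follow-up". This censoring point lies in the original WHI study. The only exception is worded "except for total mortality analyses where vital status information will be obtained from the NDI".
- Selection found: "Methods to account for non-representative enrollment using inverse sampling probability weighted tests may be employed if there is evidence of noteworthy selection".

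Objective 2 (Section 3) is "To study the longer-term effects of estrogen plus progestin and estrogen alone on cardiovascular disease, cancer and fracture incidence and mortality". Section 2.2 gives as a reason for longer follow-up of the hormone-therapy (HT) trials the need to "determine whether there is persistent harm for stroke, VT, breast cancer and other cancer incidence and mortality". Under Passive Follow-up, Section 5.3 describes the coordinating center's plan to "obtain information on vital and health status for the entire cohort, as applicable, through accessing national databases such as the National Death Index". In the Medical Records Cohort, which includes the HT women, deaths are adjudicated (Table 1 and Section 6.3).

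**The concern.** The exception names one endpoint. Take an HT woman who declined the Extension and later died of breast cancer. The total mortality analysis follows her to her death and counts it. The breast cancer mortality analysis censors her at her last original-study contact, which is the October 2004 to March 2005 close-out at the latest. Deaths by cause then cannot be reconciled with total deaths, because the same randomized women are followed for different lengths of time.

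The second branch does not repair this. Weighting is optional, and it reweights the consenters without using any non-consenter's death.

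Mortality is the outcome for which loss of follow-up through refusal is easiest to avoid, and Section 7.5 already sends non-consenters to the index for it. At stake is precision on late cause-specific deaths, which Section 2.2 names for cancer, and a coherent account of total and cause-specific mortality.

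**Working it through.** **Inputs.** Randomized HT women: 27,347 (Section 2). HT women consenting to the 2005-2010 Extension, from the lower panel of the enrollment table in Section 4.4: 6,545 + 6,243 + 3,778 + 3,867 = 20,433. Consent: 82% of the clinical trial (CT), 52,176 women, and 73% of the observational study, 63,230 women (Section 2). Original enrollment: CT 68,132, total 161,808 (Figure 1).

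**Reproducing the plan's own figures.** Eligible women = 52,176/0.82 + 63,230/0.73 = 63,629 + 86,616 = 150,246 (before rounding of the parts). Consent = 115,406/150,246 = 76.8%, against the stated 77%. Of original enrollees, 115,406/161,808 = 71.3%, against the stated 71%. So the 82% and 73% are shares of eligible women.

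**Share of HT women affected.** Not enrolled: 27,347 - 20,433 = 6,914, or 25.3% of those randomized. This count includes women who had died or could not be contacted before the invitation. The Protocol gives no HT-specific eligible number, so it must be assumed. The overall CT share is 63,629/68,132 = 93.4%.

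With E = assumed share × 27,347, the non-consenters are E - 20,433 and the fraction still observed is p = 20,433/E.

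**Precision.** The standard error of a log hazard ratio varies as 1/√(events). With equal death rates in consenters and non-consenters, events are proportional to women observed. Full coverage therefore multiplies the standard error by √p for deaths after close-out.

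| Eligible share (assumed) | E | Non-consenters | Share of E | p | √p | Cut in SE |
|---|---|---|---|---|---|---|
| 90% | 24,612 | 4,179 | 17.0% | 0.830 | 0.911 | 8.9% |
| 93.4% (overall CT) | 25,540 | 5,107 | 20.0% | 0.800 | 0.894 | 10.6% |
| 95% | 25,980 | 5,547 | 21.3% | 0.786 | 0.887 | 11.3% |
| 100% | 27,347 | 6,914 | 25.3% | 0.747 | 0.864 | 13.6% |

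The cut applies to 2005-2010 deaths taken alone. Section 7.5 also plans cumulative analyses since randomization. There, non-consenters' deaths before close-out are already counted, so the gain is smaller. The Protocol gives no death rates, so neither that gain nor the number of cause-specific deaths lost can be computed.

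**Balance by arm.** E+P 6,545/8,506 = 76.9% against placebo 6,243/8,102 = 77.1%. E-alone 3,778/5,310 = 71.1% against placebo 3,867/5,429 = 71.2%. Enrollment shows no differential loss.

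**The case against.** The strongest objection is that the Protocol never says the index search returns cause of death. Section 7.5 speaks of vital status, and Section 5.3 of vital and health status as applicable. The entire cohort in Section 5.3 may also mean Extension participants only; the clear cover for non-consenters is in Section 7.5, for vital status. This stands, and it makes the fix conditional.

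Second, deaths in HT women who take part are adjudicated. Confining cause-specific analysis to women whose cause can be adjudicated, and using the index for all-cause death, is a coherent trade-off. This also stands. It argues against replacing the adjudicated analysis, not against adding a second one.

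Third, Objective 2 does not say cause-specific, and the trials' endpoint lists are not in this document. That is so, but Section 2.2 names cancer mortality.

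Fourth, such detail often belongs in a statistical analysis plan. Here, however, Section 7.5 fixes a rule with a single exception; it does not leave the matter open.

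A reader might also infer more than the documents support:

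- *That the censoring is unconditional or biases the comparison.* It depends on the selection check, and enrollment is nearly equal by arm. That decliners were sicker is possible but not shown. Equally, a check on initial-study data cannot show whether their later deaths by cause differ.
- *That total and cause-specific mortality refer to different populations.* Both start from all randomized women under intention-to-treat. Only length of follow-up differs.
- *That women who declined re-consent in 2010 are censored in the same way.* The rule censors at last contact in the original study, so as written it does not reach women who had already joined the 2005-2010 Extension. No loss after 2010 should be computed from it.

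**Conclusion.** The point holds as one of precision and consistency. Under either branch of Section 7.5, a non-consenter's later cancer or cardiovascular death enters total mortality and is not used by cause.

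About a fifth of eligible HT women are affected; the exact share rests on an eligible fraction that the Protocol does not give for these trials. The 9% to 11% reduction in standard error holds for 5% to 10% ineligible, equal death rates, and 2005-2010 deaths alone. It makes no allowance for misclassified causes. The documents do not establish bias between arms.

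**What to change.** In Section 7.5, extend the index exception to cardiovascular and cancer mortality, where the search supplies cause of death. The sponsor must confirm that it does, and that cause may be used for women who declined.

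State the analysis: index-coded cause of death in all randomized women, consenters and non-consenters alike, followed to one common date through which the search is complete. Report it alongside the adjudicated-cause analysis in consenters, not in place of it. Using one source of cause for everyone avoids mixing coded and adjudicated causes within an analysis.

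If cause of death is not available, Section 7.5 should say so and state that cause-specific and total mortality rest on different lengths of follow-up.

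Cost: one more data item in a search already planned, one more analysis, and a few lines of text. Coded causes are less exact than adjudicated ones, which is why both analyses should be shown.
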